## 1. Abstract

**Background.** Febrile neutropenia (FN) is a worrying outcome in children receiving chemotherapy because it increments the risk of major complications, reduces quality of life and increments treatment costs. Moreover, it is the most common diagnosis in pediatric oncology patients admitted into emergency rooms and represents the second cause of hospitalization, just behind hospitalization for administration of chemotherapy.

**Problem statement:** In Mexico, incidence of FN is of 62% of children with solid tumors treated with cisplatin-based chemotherapy (CBC). Cisplatin is one of the most nephrotoxic drugs being used in clinical setting. Nephrotoxicity is usually manifested by tubular damage that causes electrolyte losses, specially of magnesium. Recently, an association of hypomagnesemia and FN apparition. This association has a biologic explanation in the fact that magnesium is a necessary cofactor for the neutrophil's diapedesis and complement activation. To our knowledge, the role of magnesium supplementation in reducing FN episodes has not been explored. With this evidence in mind, we wondered if oral supplementation with magnesium will reduce FN episodes in pediatric oncology patients treated with CBC.

**Objective.** Determine the efficacy of oral supplementation with magnesium to reduce FN episodes in pediatric oncology patients treated with CBC.

**Hypothesis.** Previous clinical trials made in adult population had report that supplementation with magnesium salts reduce episodes of hypomagnesemia between 13 to 50%. Thus, oral supplementation with magnesium oxide will reduce in 20% FN episodes in pediatric oncology patients treated with CBC.

**Materials and Methods.** Randomized Clinical Trial, open-label, parallel groups of children over nine years old with solid tumors treated with CBC at the Haemato-Oncology Department of the Hospital Infantil de México. To prove the hypothesis, it is required to randomize 107 CBC cycles to the intervention group and 107 CBC cycles to the control group. The sample size calculation was made by using the two proportions formula. Randomization of children will be performed when they receive CBC indication. Patients assigned to the intervention group will receive institutional attention protocol plus a magnesium oxide, at the moment of hospitalization discharge. Patients assigned to the control group will receive only institutional attention protocol. The follow-up of patients will be made until an episode of FN appears or until the patient comes back for another CBC cycle. FN assessment will be measured with a unique temperature  $>38.3^{\circ}\text{C}$  or a sustained temperature  $>38^{\circ}\text{C}$  over the course of an hour plus a count of neutrophils under  $1000\text{ cells/mm}^3$ . The efficacy of oral supplementation with magnesium oxide will be determined by a Relative Risks calculation with IC 95%. Moreover, Absolute Risk Reduction will be calculated, as well as Necessary Number to Treat. To adjust the principal variable a multivariate analysis will be made with a multiple logistic regression. The analysis will be made by protocol and by intention to treat.

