### *Non-inclusion Criteria*

- Patients whose parents don't accept to participate
- Patients with magnesium loss tubulopathy diagnosed previous to CBC
- Patients with hypomagnesemia previous to CBC

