To evaluate if oral supplementation with magnesium reduces secondary to CBC hypomagnesemia's, serum magnesium will be quantified before CBC and it will be measured again after the apparition of febrile neutropenia or at the moment the patients returns to another CBC cycle. Serum concentrations of magnesium below  $1.6\text{ mg/dL}$  will be considered as hypomagnesemia.

Daily maximum intake of magnesium supplements recommended for children over 9 years is  $350\text{ mg}$ . Nevertheless, the dose that will be used on this protocol is less that the recommended, it is necessary to evaluate safety of supplementation with magnesium in pediatric patients with cancer. To fulfill this purpose, each patient will be given a binnacle where they will register adverse effects that could be presented, such as diarrhea, nausea, vomit, etc.; binnacle is showed in Appendix 1. Moreover, clinical studies like hematic biometry, and other biochemical tests will be performed to determine if there is hepatotoxicity (ALT, AST and alkaline phosphatase), nephrotoxicity (creatinine) and cardiotoxicity (LDH). Biochemical determination will be made on both groups at the basal status and before every CBC cycle. Oral supplementation with magnesium will be interrupted in patients that present severe adverse reactions. All adverse reactions will be registered according NOM-220-SSA1-2015.

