### *Sample Size Calculation*

Necessary number of patients was estimated considering a normal distribution means two proportions formula, using  $\alpha = 0.05$  (two tails),  $\beta = 0.20$ , 1 on 1 proportion of assignment to each group. For calculus it was considered that non-exposed group will have a proportion of 62%, while supplemented group will have a proportion of 42% (delta

20%). With the previous conditions and considering a continuity correction, to perform the study it is required to randomize 214 cycles and assign 107 to control group and 107 to supplemented group. Calculus was done with Sample Size Calculator for Designing Clinical Research by University of California San Francisco, available at <http://www.sample-size.net/sample-size-proportions/>.

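### The arm is allocated at CBC indication but tablets start only at discharge, so FN, cancelled cycles and withdrawals before exposure can enter the open-label comparison

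*Combined protocol and SAP*

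**What the plan says.** - **Time of allocation.** The Materials and Methods paragraph of the Abstract states "Randomization of children will be performed when they receive CBC indication". Section 6, Procedure, gives the same order: the monitor reports that a patient is about to start treatment and is then told the arm for that cycle.
- **Start of exposure.** The Abstract gives the intervention arm usual care "plus a magnesium oxide, at the moment of hospitalization discharge". The Procedure describes the bottle of tablets but not when it is handed over.
- **Blinding.** None (section 6, Study Design).
- **Eligibility.** The Non-inclusion Criteria list "Patients with hypomagnesemia previous to CBC", and the Procedure says "serum magnesium will be quantified before CBC". Neither says whether the result must be in hand before allocation.
- **FN window and detection.** Follow-up ends at FN or at the return for the next cycle; no opening date is given. The one detection route described is the monitor's daily visit to the emergency department.
- **Analysis.** Section 7 divides FN cases by all cycles assigned to each arm. It plans an intention-to-treat analysis of all patients and a per-protocol analysis of those who finish, and names neither as primary. The Exclusion Criteria list withdrawal of consent during the trial.
- **Sample size.** "With the previous conditions and considering a continuity correction, to perform the study it is required to randomize 214 cycles", 107 per arm, with no allowance for loss or for cycles that never start tablets.

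**The concern.** Between allocation and discharge the planned care is the same in both arms, but everyone knows the arm. Tablets cannot prevent an FN episode that precedes the first tablet, and a cycle whose CBC is cancelled gets no tablets after that CBC. Counting such cycles under intention to treat pulls the two proportions together and costs power. Corrected power starts at 80.2%, so there is almost no margin.

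The per-protocol set carries a different risk. An intervention cycle with FN before the first tablet could be classed as not having finished the protocol, while the matching control cycle, which has no tablets to miss, stays in. That would be bias, not dilution. Withdrawals in the gap raise a similar question, because the Exclusion Criteria and the all-patients rule in section 7 point in different directions.

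**Working it through.** **Inputs from the Sample Size Calculation:** two-sided alpha 0.05; power 80%; "1 on 1 proportion of assignment to each group"; p1 = 0.62 (control); p2 = 0.42 (supplemented). **Assumed:** q, the share of FN that occurs before discharge. The documents give no value, so a range is shown. Cycles are treated as independent, as in the plan's own formula.

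**1. The plan's figure.** Mean proportion = (0.62 + 0.42)/2 = 0.52.

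Uncorrected n = [1.96·√(2·0.52·0.48) + 0.8416·√(0.62·0.38 + 0.42·0.58)]² / 0.20² = 96.8, so 97.

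Continuity-corrected n = (96.8/4)·[1 + √(1 + 4/(96.8·0.20))]² = 106.5, so **107 per arm**. The stated figure reproduces exactly. With 107 per arm, power is 83.8% uncorrected and 80.2% corrected.

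**2. Allocation at CBC indication, FN before discharge counted.** Early FN gets no benefit; later FN keeps the planned ratio 0.42/0.62. So p2 = 0.62q + 0.42(1 − q), with p1 unchanged. The same p2 results if a share q of intervention cycles never starts tablets and keeps the control rate.

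| q (assumed) | p2 | Difference, points | Power uncorrected, 107 per arm | Power corrected, 107 per arm | n per arm for 80% (corrected) |
|---|---|---|---|---|---|
| 0 | 0.420 | 20.0 | 83.8% | 80.2% | 107 |
| 2% | 0.424 | 19.6 | 82.3% | 78.5% | 111 |
| 5% | 0.430 | 19.0 | 79.9% | 75.8% | 118 |
| 10% | 0.440 | 18.0 | 75.5% | 70.9% | 131 |
| 20% | 0.460 | 16.0 | 65.3% | 60.0% | 164 |

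**3. Allocation at discharge, FN counted from then.** Cycles with early FN, a fraction e = 0.62q of all cycles, are never allocated. Among the rest, p1 = 0.62(1 − q)/(1 − e) and p2 = 0.42(1 − q)/(1 − e).

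- q = 5%: e = 0.031; p1 = 0.589/0.969 = 0.608; p2 = 0.399/0.969 = 0.412; difference 19.6 points; corrected power 78.5%. Gain: 78.5 − 75.8 = 2.7 points. Cycles consented: 214/0.969 = 220.8, about 7 more.
- q = 10%: e = 0.062; p1 = 0.558/0.938 = 0.595; p2 = 0.378/0.938 = 0.403; difference 19.2 points; corrected power 76.5%. Gain: 76.5 − 70.9 = 5.6, about 6 points. Cycles consented: 214/0.938 = 228.1, about 14 more.

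The change does not return power to 80.2%, because removing early FN also lowers the control proportion. If 62% versus 42% is meant to describe FN after discharge, 107 per arm stands.

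**4. Per-protocol set, illustration.** Suppose there is no true effect (62% in both arms) and only intervention cycles with FN before the first tablet are dropped. The intervention proportion becomes (0.62 − 0.62q)/(1 − 0.62q). At q = 5%, 10% and 20% this is 0.608, 0.595 and 0.566. The relative risk is then 0.98, 0.96 and 0.91, and the two-sided type I error about 5.4%, 6.6% and 12.1%.

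**The case against.** The strongest reply is that the documents do not show early FN entering the comparison at all. No section says when the FN window opens. Detection is through the emergency department, and the Background describes FN as something with which ambulatory patients present. FN during the chemotherapy admission may simply not be counted. This stands: the plan allows such events to enter but does not establish that they do. It also leaves the plan with a gap, because without a stated opening of the window an unwritten rule decides what counts.

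Second, under intention to treat, early FN is expected to be balanced by randomisation, so it weakens the contrast without biasing it. That is right. Allocating at CBC indication is also a legitimate treatment-policy design.

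Third, a reader might infer that the magnesium criterion removes cycles after their arm is known. The documents do not support that. Hypomagnesaemia is a bar to entry, the Exclusion Criteria contain only withdrawal of consent, and the Procedure places baseline status at CBC indication. The order of result and allocation is unstated, which calls for one clarifying sentence and no more.

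Fourth, a reader might infer that inpatient care or discharge timing responds to the known arm. It is possible, but nothing in the documents shows it.

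Finally, moving the allocation is not free, and withdrawals and per-protocol losses after discharge would remain wherever allocation is placed. Both points stand.

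**Conclusion.** The point holds in limited form. Open-label allocation comes before chemotherapy, exposure starts at discharge, and all assigned cycles form the denominator. FN, cancelled CBC or withdrawal in between can therefore dilute the intention-to-treat effect or be removed unevenly per protocol.

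The size cannot be settled from the documents. It rests on an assumed share of FN before discharge, on that FN being counted, and on later FN keeping the planned ratio. At 5% or 10%, corrected power is about 4 or 9 points below the planned 80.2%, and moving the allocation recovers about 3 or 6 of them. The per-protocol distortion is an illustration of one-sided removal, not something the plan prescribes.

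This is a worthwhile change to a stated rule. It is not an error in the sample-size arithmetic, and it does not show that the randomised comparison is broken.

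**What to change.** In the Abstract (Materials and Methods) and section 6, Procedure:

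1. Keep consent, assent and baseline at CBC indication.
2. State that the pre-CBC magnesium criterion is confirmed before allocation and is not used to drop an allocated cycle.
3. Have the monitor request the allocation on the day of discharge, only for cycles with CBC given and no FN so far.
4. Open the FN window at that point in both arms.

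In the Sample Size Calculation, say whether 62% and 42% refer to FN after discharge. If they do, 107 per arm is unchanged.

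**Costs:** a same-day request through the principal investigator, with some risk of missed allocations; about 7 or 14 more cycles consented, at the assumed 5% or 10%, to replace those lost to FN before allocation (cancelled CBC would add to this); and a result that applies to cycles free of FN at discharge.

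If the sponsor keeps allocation at CBC indication, the plan should state when the FN window opens, how FN during the chemotherapy admission is found and counted, that intention to treat is primary, and how withdrawals and cycles that never start tablets are handled. That settles the ambiguity but leaves any dilution in place.

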## **2. Background**

### **Cancer in pediatric patients**

Cancer it's a major health problem on Mexican pediatric population. The incidence of cancer cases in our country has been estimated in 126 cases/million/year and it's estimated that there are between 5000 and 6000 new cancer cases per year in children, whereas the incidence ratio is about 9 cases per 100 000 children for non-insured population. Approximately, 40% of all neoplasms presented in Mexican childhood are solid tumors. The age of apparition of cancer in Mexican pediatric population fluctuates between 2 and 14 years old.

Secondary to the improvement of diagnosis methods and treatments, the survival of children with cancer has been incremented to 80% to 5 years. In our country, efforts made in the last year have created a tendency to upward survival.

### **Cancer treatment**

Cancer treatment options depends on cancer type, stage, and other factor such as age, and general health status of each patient. Treatment is founded in three major strategies: surgery, radiotherapy and chemotherapy. Chemotherapeutic drugs work causing cellular death in diverse ways. Genotoxic agents are drugs that damage DNA, interfere with DNA replication, stop cellular division or induce cellular apoptosis. However, chemotherapeutic drugs also affect non-cancerous cells, contributing to their toxicity. Fast regenerating cells, like the ones from the bone marrow and the walls of the intestines, tend to be more affected, causing neutropenia and mucositis, respectively. Thus, the death of non-cancerous cells constitutes the most frequent adverse reaction of chemotherapy. About 75% of pediatric patients with cancer had suffered at least one adverse reaction associated to chemotherapy,

and 36% had suffered a severe adverse reaction that threatens their life or permanently incapacitates them.

Cisplatin is an irreplaceable drug in the treatment of diverse solid tumors in both adults and children. At the Hospital Infantil de México Federico Gómez, chemotherapeutic schemes that include cisplatin as a first line treatment for solid tumors like osteosarcomas, hepatoblastomas and germ cells tumors.

### **Febrile Neutropenia**

Neutropenia is a common adverse reaction associated to cytotoxic chemotherapy. Diminish of neutrophils count increases the risk of opportunistic infections that manifests with fever. Therefore, ambulatory patients with cancer come to emergency rooms with febrile neutropenia (FN) induced by chemotherapy, an emergency that requires immediate evaluation and treatment. In the US, more than 60000 patients with cancer (7.38 cases/1000 patients with cancer) are hospitalized annually for febrile neutropenia and related infections, with a mortality that rises to the 6.8%. Nonetheless, it's been reported that FN mortality can fluctuate between 2.3 and 14% depending on the type of tumor, the age of the patient and the studied population.

In pediatric population with cancer, the FN is an important adverse reaction because it increments the risk of major complications, it reduces the quality of life and it increments the treatment costs. Moreover, FN is the most common diagnosis in children with cancer admitted into emergency room and the second cause of hospitalization, just behind hospitalization for chemotherapy. In Mexico, incidence of FN is about 62% of children with solid tumors treated with cisplatin-based chemotherapy (CBC). Likewise, hospital stay is around 6 and 9 days with an approximated cost of \$100,000 MXN per episode.

## Magnesium

Magnesium is the fourth most abundant cation in organisms and has a role as a cofactor of 300 enzymatic systems, especially in reactions where ATP (adenosine triphosphate) intervenes, since it stabilizes negative charges of triphosphates. Magnesium is necessary for generation of energy in glycolysis, it forms part of the ATP-Mg complex, and is an important enzymatic cofactor. In mitochondria, enzymes use ATP and ADP-magnesium chelate as substrates for phosphate transference.

Magnesium's presence is important to maintain an adequate supply of necessary nucleotides for the synthesis of DNA and RNA that produces in cellular proliferation. Likewise, cellular replication needs protein synthesis, that diminishes with the depletion of magnesium supply.

Magnesium is most abundant in the bones (50-60%) and in minor proportion in muscles. Just 1-2% is found in extracellular liquid, and the rest is localized in the inside of cells, where is the second most abundant cation, after Potassium. Magnesium corporal deficiency appears with concentrations minor to 1 mg/dL. Approximately, 25% of serum magnesium is bonded to proteins, most to albumin; 15% forming other complexes; and 60% is free; the ionized form of magnesium is the one with physiological activity.

With an average diet people ingests about 300 mg/day of elemental magnesium. Near 30-40% of ingested magnesium is absorbed long in the gastrointestinal tract, mainly in the jejunum and ileum. Before a deficient magnesium ingest on the diet, non-saturable passive mechanisms of absorption and saturable active transport increase intestinal absorption around 70-80%.

Kidney is the main organ involved in magnesium homeostasis. Renal management of magnesium is a filtration-reabsorption process. No description of tubular secretion of

magnesium has been described. Approximately, 65% of filtered magnesium is reabsorbed on Henle's loop, and between 20-30% on proximal convoluted tubule. Magnesium reabsorption in the proximal convoluted tubule seems to be passive and follows changes in water and sodium reabsorption, moreover is associated to the fluid flux rate. On Henle's circuit, it seems to be an additional active transport: there is decrease in magnesium's reabsorption on this segment independently of the sodium chloride transport in hypermagnesemia or hypercalcemia. Magnesium's renal excretion is around 100 mg/day, representing less than 3% of magnesium's glomerular filtration.

Magnesium imbalance can be found in type 2 diabetes, chronic renal failure, nephrolithiasis, osteoporosis, aplastic osteopathy, migraine, cardiac disease and hypertension. There are three described physiological mechanisms of magnesium deficiency: poor intestinal absorption, increased urinary lost or intracellular changes of this cation.

### **Cisplatin-induced hypomagnesemia**

Cisplatin is one of the most nephrotoxic drug used in clinical setting. Cisplatin-induced hypomagnesemia has an origin in the direct damage on magnesium reabsorption mechanisms at Henle's loop and distal tubule. The incidence of hypomagnesemia in children that receive cisplatin is around 40%.

Due to the importance of maintenance of adequate magnesium levels different strategies have been proposed. Studies done on guinea pigs have shown that a rich magnesium diet can prevent severe cisplatin-induced hypomagnesemia.

Most of clinical studies conducted on this manner have focused on intravenous administration of magnesium to prevent and treat cisplatin-induced hypomagnesemia. Nevertheless, there is evidence showing that oral supplementation with magnesium salts can be effective to prevent hypomagnesemia. Willox et al., reported that oral supplementation

with magnesium citrate, between chemotherapy cycles in patients with testicular cancer receiving cisplatin, increases significantly magnesium concentration in comparative with a group of patients that didn't receive the supplement. Martin et al., demonstrated that prophylactic oral supplementation with magnesium pidolate reduced in 50% the episodes of hypomagnesemia in patients treated with four cycles of cisplatin. In Iran, oral supplementation with magnesium oxide reduced in 13% the prevalence of hypomagnesemia in adult patients with cancer treated with cisplatin.

### **Magnesium's role in infectious process**

Magnesium plays an important role on immune response in different ways: it is a necessary cofactor for immunoglobulin and C3 convertase synthesis, it participates in immune cell adherence, antibody-dependent cytolysis, lymphocytes union, macrophage response to lymphokines, adherence between T lymphocytes and B lymphocytes, adherence of P substance to lymphoblast, and antigen to RNA binding of macrophages.

Low serum concentration of magnesium had been associated with acute bacterial infections, although low association had been made with viral acute infections. In the same sense, hypomagnesemia has been associated with development of sepsis in critically ill patients at Intensive Care Units. Moreover, it has been demonstrated that low intake of magnesium in the diet alters the morphology and the immune response of gut mucosae in mice.

Recently, our team has reported an independent association between hypomagnesemia and FN in pediatric patients with solid tumors treated with cisplatin-based chemotherapy (RR = 8.20, CI95% [1.81-37.14]). This evidence suggests that if reduction of serum concentrations of magnesium is prevented, the incidence of FN can be diminished. Supporting this hypothesis, Willox et al., showed that supplementation with magnesium

citrate presents a tendency to reduce FN episodes (about 15%) in adult patients with testicular cancer treated with cisplatin. However, the small number of patients included in the study, and the fact that the study wasn't designing to prove reduction of apparition of FN limited the statistical power of these findings.

